3.5.1.3 Handling of Dropouts and Missing Data

RSV LRTI that occurs through 150 days post dose will contribute to the primary efficacy analysis. For subjects who do not have a medically attended RSV LRTI and are not followed through 150 days post dose, their event status will be imputed assuming the observed placebo medically attended RSV LRTI rate conditional on stratification factors using multiple imputation techniques as described in the following paragraphs.

The primary analysis uses Poisson regression with robust variance requires a subject-level dataset. A repeated imputation approach is introduced to impute medically attended RSV LRTI status for missing observations at the subject-level for the model fitting. By incorporating the between-imputation variance, a reliable statistical inference in both hypothesis testing and CI estimation of the treatment effect is expected through the repeated imputation (Little and Rubin, 2002). In the primary analysis the missing outcome for subjects who dropped out prior to reaching Day 150 post dose without a medically attended RSV LRTI event will be imputed per stratum determined by the two stratification factors using placebo event rate. The imputation and subsequent analysis will be carried out using SAS PROC MI (Monotone Logistic Regression Method) and SAS PROC MIANALYZE. The detailed imputation steps are described as follows.

- Step 1: For the subjects in the MEDI8897 arm who do not have an RSV LRTI and are not followed through 150 days post dose, their treatment code of “MEDI8897” will be substituted with “placebo” to ensure the placebo RSV LRTI rate is applied in the imputation for the MEDI8897 dropouts adjusted for their stratification values. The imputation will be executed using SAS Proc MI (eg, logistic regression with the recoded treatment term and stratification factors).
- Step 2: The original treatment code will be restored after the RSV LRTI event statuses have been imputed. A complete dataset comprises the imputed RSV LRTI status and observed RSV LRTI status.
- Step 3: Analyze the complete dataset using a Poisson regression model with robust variance to estimate the relative risk on the incidence of medically attended RSV LRTI between MEDI8897 and placebo, with the term of treatment group and two stratification factors. The point estimate of log-transformed RR and its variance will be extracted from the model.
- Steps 2-3 will be repeated 20 times. SAS procedure PROC MIANALYZE will be used to combine inferences from the 20 completed datasets, that will result in a combined point estimate of log-transformed relative risk and the variance. The random seed is 12345.

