4.8.3.1 Primary Efficacy Analysis

The incidence of RSV LRTI (inpatient and outpatient) during 5 months of the RSV season will be based on RSV test results (performed centrally via RT-PCR) and objective clinical LRTI criteria and will be summarized by treatment group. For subjects with multiple medically attended RSV LRTI events, only the first occurrence will be used in the primary analysis.

The primary efficacy analysis of the primary endpoint will be conducted with the ITT Population. LRTI caused by RSV that occurs prior to discontinuation from participation in the study will contribute to the primary efficacy analysis. For subjects who do not have an RSV LRTI prior to discontinuation from participation, their event status will be imputed assuming the observed placebo RSV LRTI rate. This will be implemented by imputations based on repeated simulations and will be described in the Statistical Analysis Plan. A Poisson regression model with robust variance (Zou, 2004) will be used as the primary

efficacy analysis model to compare the incidence of medically attended RSV LRTI between MEDI8897 and placebo, including treatment group, age at the time of randomization (ie, ≤ 3 months, $> 3 - \leq 6$ months, > 6 months) and dichotomous temperate (northern and southern) hemispheres as covariates. In addition, the 2-sided p-value and corresponding 2-sided 95.1% CI on the relative risk will be provided from the model. Relative risk reduction is defined as $(1 - P_n/P_s)$ where P_n is the incidence of RSV LRTI during 5 months of the RSV season in the MEDI8897 group and P_s is the incidence of RSV LRTI during 5 months of the RSV season in the placebo group generated from the model. Statistical significance will be achieved if the 2-sided p-value is ≤ 0.05 .

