2.4 Sample Size

The sample size of 1,500 subjects is necessary based on advice from the United States Food and Drug Administration US FDA requesting that 1,000 preterm infants be exposed to MEDI8897 in this Phase 2b study. This sample size has approximately > 99% power to detect 70% relative-risk reduction, assuming a placebo group medically attended RSV LRTI incidence of 8%. Power calculations are based on a Poisson regression model with robust variance (Zou, 2004) comparing MEDI8897 50 mg versus placebo, with 2-sided, $\alpha = 0.05$.

- The 70% relative-risk reduction assumption is based on a placebo-controlled study in Native American infants in which there was 87% relative reduction in the incidence of RSV hospitalization (11.3% placebo; 1.5% motavizumab; $p < 0.001$) and 71% relative reduction in the incidence of outpatient RSV LRTI (10.0% placebo; 2.9% motavizumab; $p < 0.001$) in infants who received motavizumab prophylaxis (O'Brien et al, 2015)

In order to evaluate risk, a sample size of 1,000 subjects exposed to MEDI8897 will provide a 90% probability of observing at least one AE if the true event rate is 0.2%; if no AEs are observed, this study provides 95% confidence that the true event rate is < 0.3%.

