3.5.1 Primary Efficacy Endpoint and Analyses

3.5.1.1 Primary Efficacy Endpoint

The primary endpoint is the incidence of medically attended RSV LRTI (inpatient and outpatient) through 150 days post dose. For subjects with multiple medically attended RSV LRTI events (inpatient or outpatient), only the first occurrence will be used in the primary analysis.

The determination of medically attended RSV LRTI will be based on objective clinical LRTI criteria (described in the Protocol [Section 4.3.1.1](#) and SAP [Appendix 1](#)) and RSV test results obtained from analyzing the respiratory secretions using a validated RSV RT-PCR assay for the detection of RSV A or RSV B performed in a central laboratory. These LRTI events may occur in the inpatient or outpatient visit setting.

Prior to database lock for the primary analysis, a blinded review of data will be undertaken to determine an analysis window such that all positive results will be counted as a medically attended RSV LRTI if they occurred in a respiratory sample collected within this window relative to the initial date seen by the healthcare provider (eg, admission/deterioration date associated with the event, urgent care visit, outpatient ED visit, or outpatient clinic visit). The actual window used will be documented prior to unblinding. In addition, deaths that can be demonstrated as caused by RSV (by autopsy or clinical history and virologic evidence) will also be considered as primary medically attended RSV LRTI events.

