3.5.1.6. Sensitivity Analyses for Subjects who are Not Followed through 150 Days Post Dose

Sensitivity analyses for RSV LRTI through 150 days post dose will be performed to address subjects who do not have an RSV LRTI and are not followed through 150 days post dose through various approaches of missing data imputation are described as follows:

1. Subjects who do not have an RSV LRTI and are not followed through 150 days post dose will be counted as having not met the RSV LRTI endpoint.
2. Impute the missing values in each treatment group using 2-times the placebo RSV LRTI event rate through 150 days post dose (ie, Bernoulli distribution with expected value equal to 2-times placebo RSV LRTI event rate).
3. Tipping point analysis by imputing the missing values in the MEDI8897 arm using 2-times the placebo event rate through 150 days post dose and imputing the missing

values in the placebo arm with the placebo rate (ie, Bernoulli distribution with expected value equal to 2 or 1-times placebo RSV LRTI event rate).

4. Tipping point analysis by imputing the missing values in the MEDI8897 arm using 3-times the placebo event rate through 150 days post dose and imputing the missing values in the placebo arm with the placebo rate (ie, Bernoulli distribution with expected value equal to 3 or 1-times placebo RSV LRTI event rate)
5. Subjects who do not have an RSV LRTI and are not followed through 150 days post dose will be counted as having met the RSV LRTI endpoint.
6. Multiple imputations
7. Impute the missing values in each treatment group using 1-time, 2-time, and 3-time the overall placebo event rate in single imputation approach.

The sensitivity analyses 2-4 will be conducted following the steps below:

- Step 1: Determine the observed placebo RSV LRTI rate through 150 days post dose, which is calculated as the proportion of all randomized placebo subjects with observed RSV.
- Step 2: Impute the event status for subjects who do not have an RSV LRTI and are not followed through 150 days post dose in each treatment arm or the MEDI8897 arm only (depending on the sensitivity analysis planned above) using the Bernoulli distribution with X-times the observed placebo RSV LRTI rate without involvement of stratification factors.

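### The primary imputation gives infants who leave part-way the full 150-day placebo risk, ignoring days already observed event-free, so both incidences and the primary relative risk reduction are modestly biased

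*SAP*

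**What the plan says.** The primary endpoint is the "incidence of medically attended RSV LRTI (inpatient and outpatient) through 150 days post dose" (SAP v5, 3.5.1.1).

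Protocol 4.8.3.1 sets the principle for infants who discontinue without an event: "their event status will be imputed assuming the observed placebo RSV LRTI rate". SAP v5 section 3.5.1.3 implements it. The infants concerned are identified as follows: "For subjects who do not have a medically attended RSV LRTI and are not followed through 150 days post dose". Their status "will be imputed per stratum determined by the two stratification factors using placebo event rate". MEDI8897 dropouts are temporarily recoded as placebo, and the model is a "logistic regression with the recoded treatment term and stratification factors". On the repetition the SAP says: "Steps 2-3 will be repeated 20 times"; the results are then pooled.

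The sensitivity analyses in SAP v5 section 3.5.1.6 that use multiples of the placebo rate impute "using the Bernoulli distribution with X-times the observed placebo RSV LRTI rate without involvement of stratification factors". Section 3.5.2.3 uses similar steps for RSV hospitalization. None of these steps uses follow-up time, although 3.5.1.4 already derives it for each infant.

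**The concern.** An event before dropout counts as an event. If there was none, the rule applies the whole 150-day risk again from the day of dropout. A placebo dropout at day c is thus assigned a total risk of F(c) + [1 − F(c)] × F(150), where F is the placebo cumulative risk. For any c after Day 0 this exceeds F(150), the placebo risk that the plan says it assumes.

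This is separate from the choice to give MEDI8897 dropouts placebo risk. That choice is prespecified, reference-based and deliberately cautious. The missing conditioning on observed time also affects placebo dropouts, where raising the incidence is not cautious.

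At stake is the headline estimate. The primary RRR, confidence interval and p-value all come from the imputed datasets, so they depend partly on when infants leave and from which arm.

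**Working it through.** **Inputs.** From SAP 2.4: placebo risk p0 = 8%, and RRR 70%, so MEDI8897 risk p1 = 0.08 × 0.30 = 2.4%; two-sided alpha 0.05. From SAP 2.2: 1000 MEDI8897 and 500 placebo infants. Window: 150 days. Dropout rate and timing are not given, so I assume 1% to 10% and vary the timing. Constant hazard is also assumed, and strata are ignored.

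**The plan's own figure.** The SAP states power above 99%. For log RR, SE² = 0.92/(500 × 0.08) + 0.976/(1000 × 0.024) = 0.0230 + 0.0407 = 0.0637, so SE = 0.252. Then |ln 0.30|/SE = 1.204/0.252 = 4.77 and power = Φ(4.77 − 1.96) = 99.8%. The figure is reproduced.

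**Remaining placebo risk.** With S_p(t) = 0.92^(t/150), the risk left after day c is 1 − S_p(150)/S_p(c) = 1 − 0.92^((150−c)/150). This gives 7.5% at Day 10, 4.1% at Day 75, 3.2% at Day 91 and 0.55% at Day 140. The SAP rule gives about 8% in every case.

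**Example: 5% dropout in each arm, uniform over 150 days.** The mean probability of being event-free at dropout is 0.9594 for placebo and 0.9880 for MEDI8897.

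- Placebo: missing = 500 × 0.05 × 0.9594 = 23.99. Observed events = 500 × (0.95 × 0.08 + 0.05 × 0.0406) = 39.01. Rate among infants with known status = 39.01/(500 − 23.99) = 8.20%.
- MEDI8897: missing = 1000 × 0.05 × 0.9880 = 49.40. Observed events = 1000 × (0.95 × 0.024 + 0.05 × 0.0120) = 23.40.
- SAP rule: imputed events 1.97 (placebo) and 4.05 (MEDI8897). Incidences 40.98/500 = 8.20% and 27.45/1000 = 2.75%. RRR 66.5%.
- Residual-risk rule: imputed events 0.99 and 2.01. Incidences 40.00/500 = 8.00% and 25.41/1000 = 2.54%. RRR 68.2%.

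The true placebo risk is 8.00%. The residual-risk rule recovers it; the SAP rule does not.

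**Varying the dropout rate (equal arms, uniform timing).**

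| Dropout | Imputed events, SAP / residual | RRR, SAP / residual | Shift (points) |
|---|---|---|---|
| 1% | 1.2 / 0.6 | 69.3% / 69.6% | −0.3 |
| 2% | 2.4 / 1.2 | 68.6% / 69.3% | −0.7 |
| 5% | 6.0 / 3.0 | 66.5% / 68.2% | −1.7 |
| 10% | 12.3 / 6.0 | 63.0% / 66.5% | −3.5 |

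Power stays above 99% under either rule at 2%, 5% and 10%.

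**Varying the timing (5%, equal arms).** The ratio of imputed events, SAP to residual, is 1.0 if all leave at Day 1, 1.20 for uniform dropout over Days 0–50, 1.26 at Day 31, 2.55 at Day 91 and 6.0 for uniform dropout over Days 100–150. Under uniform dropout over 150 days, a rising hazard gives 1.5 and a falling hazard 3.0. The SAP rule returns an RRR of about 66.5% whatever the timing. The residual-risk RRR runs from 66.5% (Day 1) to 69.4% (Days 100–150).

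**Unequal dropout (MEDI8897 / placebo).**

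| True effect | Dropout | Timing | RRR, SAP | RRR, residual |
|---|---|---|---|---|
| None (8% both) | 2% / 10% | uniform | +3.9% | 0 |
| None (8% both) | 10% / 3% | uniform | −3.3% | 0 |
| Design | 2% / 10% | uniform | 69.8% | 69.3% |
| Design | 2% / 10% | Days 100–150 | 70.5% | 69.8% |
| Design | 3% / 10% | uniform | 68.9% | 68.9% |
| Design | 10% / 3% | uniform | 62.0% | 66.5% |

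At the design effect the two inflations roughly cancel when placebo dropout is p0/p1 = 0.08/0.024 = 3.3 times MEDI8897 dropout, as the 3% / 10% row shows.

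**The case against.** The rule is prespecified in both documents, and the SAP plans analyses that avoid it. Section 3.5.1.4 repeats the Poisson model with a log follow-up-time offset and no imputation, runs a stratified CMH test without imputing events for MEDI8897 dropouts, and plans Kaplan-Meier curves with stratified tests on observed events. Sensitivity analysis 1 counts dropouts as non-events. In the 5% example it gives 39.01/500 = 7.80% and 23.40/1000 = 2.34%, an RRR of 70.0%, so it and the primary result bracket 68.2%. A material dependence on the rule would be visible.

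This stands as mitigation. It does not correct the primary estimate. The offset, CMH and Kaplan-Meier analyses drop the placebo-risk assumption, and sensitivity analysis 1 sets the remaining risk to zero. No planned analysis combines placebo risk with observed time.

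Three stronger readings are tempting, and the documents do not support them:

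- A reader might infer that imputed events are about doubled. That needs dropout spread evenly over 150 days and a flat hazard; neither is stated. The factor runs from 1.0 to about 6. Infants randomized but not dosed are not followed (Protocol 4.1.6), and for them the full risk is correct.
- A reader might infer that the primary result is simply wrong. At 2% to 5% equal, uniform dropout the shift is 0.7 to 1.7 points toward no effect, no effect is created under the null, and power is hardly touched.
- A reader might infer that the rule could favour the product materially. At the design effect this needs placebo dropout more than about 3.3 times MEDI8897 dropout, and the gain was under 1 point in every scenario tried. Nothing in the plan of this double-blind, single-dose trial points to such imbalance.

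**Conclusion.** The concern holds as a modest bias in the primary estimate. The rule discards observed event-free time and assigns part-way dropouts more than the placebo risk that the plan says it assumes, in both arms. With equal dropout the RRR moves toward no effect, by 0.7 points at 2%, 1.7 at 5% and 3.5 at 10% under uniform timing; at 5% the range across the timings tried is 0 to 2.9 points. With unequal dropout the direction depends on which arm loses more infants, and a non-zero RRR can appear when there is no effect.

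These sizes rest on assumed dropout rates, timing and a constant hazard at the design risks. In the equal-dropout scenarios checked, power stays above 99%. The change is worth making because the rule feeds the headline figure and is easily corrected.

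**What to change.** Keep the placebo-risk assumption. In SAP 3.5.1.3 Step 1, draw each event-free dropout's status with probability 1 − S_p(150)/S_p(c). Here c is the last day of efficacy observation, with c = 0 stated explicitly for undosed infants. S_p is a parsimonious placebo event-free curve, for example piecewise exponential, with main effects for age group and hemisphere and parameters redrawn for each imputation. Use the same conditioning, with the multipliers where they apply, in 3.5.1.6 and 3.5.2.3. Report dropout timing by arm, and keep the full-window rule as a sensitivity analysis.

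Cost: a SAP revision and a programming change before unblinding, with a matching clarification of Protocol 4.8.3.1. The placebo-rate principle there is unchanged, and follow-up time is already derived in 3.5.1.4. The downside is a slightly more complex imputation model, fitted to about 500 × 0.08 = 40 expected placebo events; hence main effects only, not a separate curve for each of the six strata.

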3.5.1.4 Additional Analyses of the Primary Efficacy Endpoint

The following analyses will be conducted on the ITT population.

To allow for differences in follow-up time, the primary analysis using a Poisson Regression with robust variance will be repeated, adjusting for the same covariates as well as log (follow-up time) as an offset. Since the follow-up time is adjusted in the model, there is no missing imputation for this analysis. Calculation of follow-up are detailed as follows:

- For subjects who meet the medically attended RSV LRTI endpoint within 150 days post dose, the follow-up time will be calculated as (Date of Onset of RSV LRTI) – (Date of Dosing) +1.
- For subjects who do not experience a medically attended RSV LRTI event within 150 days post dose, the efficacy follow-up will be determined based on the following:
 - If an end of study date occurs within 150 days post dose (or end of study date is missing and last assessment date occurs within 150 days post dose), the efficacy follow-up will be calculated as (Date of End of Study or Date of Last Assessment, whichever is later) – (Date of Dosing) +1.

- If an end of study date occurs after 150 days post dose (or end of study date is missing and last assessment date is after 150 days post dose), the efficacy follow-up will be censored (at 151 days).

A CMH test stratified by hemisphere and age group at randomization (ie, age ≤ 3 months, age > 3 to ≤ 6 months, age > 6 months) will be used to compare between treatment groups through 150 days post dose as the key secondary analysis for the primary endpoint. SAS procedure of PROC FREQ with CMH option will be used to perform the analysis. The relative risk of MEDI8897 over placebo for the incidence of medically attended RSV LRTI events and the 95% CI will be obtained from the SAS procedure. The percent of RR reduction and the 95% CI will be reported following the relationship of RR reduction (%) = $(1 - \text{relative risk}) * 100\%$. This analysis will be performed without any imputation of event for MEDI9987 subjects who dropped out the study prior to Day 150 post dose and did not have a medically attended RSV event.

A Kaplan-Meier curve for time to first medically attended RSV LRTI will be generated based on observed events. The algorithm for time-to-event calculation is the same as to that for follow-up time (see previous). Treatment group differences in time-to-first medically attended RSV LRTI will be compared using the stratified log-rank test and Wilcoxon test with two stratification factors as the strata.

In addition, all observed medically attended RSV LRTI events and the corresponding incidence rates will be tabulated by Inpatient (primary hospitalization, nosocomial hospitalization) and Outpatient, for the latter category, further presentation will be made by different medical settings: outpatient clinic, urgent care clinic, and emergency department visits for subjects who did not have a hospitalization due to RSV.

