6.3 Study Timetable and End of Study

An individual subject will be considered to have completed the study if the subject was followed through the last protocol-specified visit/assessment (including telephone contact).

Subjects will be considered not to have completed the study if consent was withdrawn or the subject was lost to follow-up (see Sections 4.1.5 and 4.1.6).

The end of the study (“study completion”) is defined as the date of the last protocol-specified visit/assessment (including telephone contact) for the last subject in the study.

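### SAP 3.5.1.4 ends efficacy follow-up at the end-of-study date, so days after an infant's last contact can count as observed event-free time in the offset Poisson and Kaplan-Meier analyses

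*SAP*

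**What the plan says.** All SAP references are to version 5.

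- **Follow-up rule (SAP 3.5.1.4), end-of-study date beyond the window.** For an infant with no event: "If an end of study date occurs after 150 days post dose", then "the efficacy follow-up will be censored (at 151 days". The last assessment date decides only when the end-of-study date is missing.
- **Follow-up rule, end-of-study date inside the window.** Follow-up runs to "Date of End of Study or Date of Last Assessment, whichever is later".
- **Where the rule applies.** It is written for the Poisson model with log follow-up time as an offset, of which the SAP says: "Since the follow-up time is adjusted in the model, there is no missing imputation for this analysis". For Kaplan-Meier and its tests: "The algorithm for time-to-event calculation is the same as to that for follow-up time".
- **Primary imputation (SAP 3.5.1.3).** Event-free infants who "are not followed through 150 days post dose, their event status will be imputed assuming the observed placebo" rate within strata. The section gives no date basis for this condition and does not refer to 3.5.1.4. The sensitivity analyses in 3.5.1.6 address the same group.
- **Lost infants (Protocol 6.3).** "Subjects will be considered not to have completed the study if consent was withdrawn or the subject was lost to follow-up". Neither document says which date becomes the end-of-study date for such an infant.

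**The concern.** The offset model is there to allow for unequal follow-up, and follow-up time takes the place of imputation in it. It does that job only if the time counted is time during which an RSV LRTI could have been detected. An end-of-study date may be an administrative date. Choosing the later of two dates shows that the SAP itself expects end of study and last assessment to differ. When they do, an infant nobody could reach stays in the denominator and the risk set as if observed and well.

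A second question follows for the primary analysis. Section 3.5.1.3 leaves its trigger undefined, and 3.5.1.4 contains the only explicit follow-up calculation in the SAP. If a programmer borrowed it, infants lost early but closed late would be analysed as observed non-events. They would then leave both the placebo-rate imputation and every scenario in 3.5.1.6, so no planned sensitivity analysis would reveal them.

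**Working it through.** **1. Design inputs and the plan's own figure.** SAP 2.4 gives placebo incidence 8% and a 70% reduction, hence 0.30 × 8% = 2.4% on MEDI8897, with 1,000 and 500 infants and two-sided alpha 0.05. On the log relative-risk scale:

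SE = √[(1 − 0.08)/(500 × 0.08) + (1 − 0.024)/(1000 × 0.024)] = √(0.0230 + 0.0407) = 0.252

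Power = Φ(|ln 0.30|/0.252 − 1.96) = 99.75%; a pooled two-proportion test gives 99.57%. Both agree with the stated figure of more than 99%.

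**2. The rule applied to one infant.** Last seen Day 31, closed Day 200: observed follow-up is 31 days, credited follow-up 151, excess 151 − 31 = 120. Last seen Day 91: excess 60.

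**3. Effect on the offset model.** Let a share f of an arm be last seen on Day 31 and closed after Day 150. Ignoring the time cut off by events, true person-time as a fraction of credited person-time is g = (1 − f) + f × 31/151, and the arm's event rate is understated by that factor.

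| f | g | Reduction if both arms affected equally | MEDI8897 arm only (1 − 0.30g) | Placebo arm only (1 − 0.30/g) |
|---|---|---|---|---|
| 2% | 0.984 | 70.0% | 70.5% | 69.5% |
| 5% | 0.960 | 70.0% | 71.2% | 68.8% |
| 10% | 0.921 | 70.0% | 72.4% | 67.4% |

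Equal shares cancel in the ratio and lower only the absolute rates. Unequal shares move the estimate in either direction. Kaplan-Meier is affected in the same way, through risk sets that are too large after the last contact.

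**4. Conditional case: the same rule also decides who is imputed.** Assume a constant hazard, share f in both arms, and last contact at fraction t of the window.

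- Credited as event-free: p[(1 − f) + ft]. The bracket cancels, so the reduction stays at 70.0%.
- Imputed at the placebo rate: p(1 − f) + f[pt + (1 − pt) × 0.08].

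For f = 5%, t = 0.2:

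- Placebo: 0.076 + 0.05 × (0.016 + 0.984 × 0.08) = 0.0807
- MEDI8897: 0.0228 + 0.05 × (0.0048 + 0.9952 × 0.08) = 0.0270
- Ratio 0.335, reduction 66.5%

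| f (both arms) | Credited | Imputed, t = 0.2 |
|---|---|---|
| 1% | 70.0% | 69.3% |
| 2% | 70.0% | 68.6% |
| 5% | 70.0% | 66.5% |
| 10% | 70.0% | 63.1% |

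Varying t from 0 to 0.5 changes the imputed 10% figure only between 63.0% and 63.3%. If only the MEDI8897 arm were affected (t = 0.2), credited against imputed would be 70.5% and 68.5% at 2%, 71.2% and 66.2% at 5%, and 72.4% and 62.4% at 10%. With equal shares, power stays at about 98.8% or above, ignoring between-imputation variance.

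**5. Stability between the two analyses.** An infant lost early whose end-of-study date is still missing at the Primary Analysis is measured by last assessment. If the record is closed after Day 150 before the Final Analysis, the same infant moves to 151 days when SAP 3.5 refreshes the efficacy analyses, with no new efficacy information.

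**The case against.** A reader might infer that late-closed infants definitely escape the planned imputation, and that the SAP therefore contradicts the protocol. The documents do not support that. The rule sits in a section whose first analysis involves no imputation, and 3.5.1.3 has its own trigger and does not cite the rule. Read plainly, an infant last reached on Day 31 was not followed to Day 150 and would be imputed. The SAP also uses visit-based status elsewhere (the Day 151 visit denominators in 3.5.1.5 and 3.5.3), which a programmer could adopt, and section 1 defers specifications to a programming plan that is not available here. Protocol 4.8.3.1 keys imputation to discontinuation from participation, not to last ascertainment, so there is no direct conflict of wording.

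Other points narrow the issue further:

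- If the end-of-study date recorded for a lost infant is the date of last contact, the problem disappears. The documents do not settle this.
- For withdrawals, Protocol 4.1.5 has caregivers asked about adverse events, so that date may itself be a valid ascertainment. The exposure is mainly among infants lost to follow-up.
- With two-weekly calls to Day 151, a gap from Day 31 means about eight missed calls (120/14 ≈ 8.6) and missed Day 91 and Day 151 visits. Nothing shows how often this would occur.
- In step 4 the true reduction is 70%, so crediting does not bias the estimate when loss is equal and non-informative. It removes conservatism that the plan chose to build in.

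These points dispose of the stronger reading and limit the size. They leave the 3.5.1.4 rule as it stands: followed literally, a late end-of-study date overrides an early last assessment.

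**Conclusion.** The point holds for the offset Poisson model and for the Kaplan-Meier, log-rank and Wilcoxon analyses. The SAP text credits follow-up from a date that need not be an observation, by up to 120 days for an infant last seen on Day 31. The effect on the rate ratio is nil if the arms are equally affected. At 5% affected in one arm only, it is about 1.2 points in either direction.

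For the primary analysis the finding is an undefined imputation trigger, not a demonstrated error. Only if the 3.5.1.4 rule were used there would the reported reduction exceed the planned one, by about 0.7 points at 1% affected, 3.5 at 5% and 7 at 10%, with equal shares, 8% against 2.4%, and every affected infant closed after Day 150. The significance conclusion would barely change. The affected share is an assumption throughout, since the documents state neither a dropout rate nor how end-of-study dates are assigned. The correction is worth making because it settles the rule before the size of the problem is known.

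**What to change.** - **SAP 3.5.1.4.** For event-free infants, end follow-up at the last date LRTI status was ascertained: a study visit, an illness visit, a completed scheduled call, or a withdrawal contact at which adverse events were asked about. Keep the existing 151-day cap, and drop the end-of-study date from the calculation.
- **One definition of follow-up through 150 days.** Count an infant as followed if the Day 151 visit was completed within its protocol window or if any later contact was completed. Requiring contact on or after Day 151 would be wrong: the window is ±7 days, so an infant seen on Day 146 would be imputed despite completing the visit.
- **Use that flag in 3.5.1.3, 3.5.1.4 and 3.5.1.6**, so that the primary imputation, the additional analyses and the sensitivity analyses agree on who was followed.
- **Report by arm** the number of infants whose last contact precedes Day 150 but whose end-of-study date follows it. If there are none, this late-closure problem does not arise.

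The cost is SAP wording and one derived date from visit and call data already scheduled. No study procedure changes. The estimate may become slightly less favourable if some infants move from event-free to imputed.
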